17.2. SECONDARY EFFICACY

Each of the secondary endpoints described below will be analyzed in the FAS and PPS:

- Progression-free survival (PFS), based on blinded central radiology assessment
- Overall Survival (OS)
- Objective Response (OR), based on the investigator's radiographic assessment
- Disease control (DC), based on the investigator's radiographic assessment
- Duration of Objective Response (DOR), based on the investigator's radiographic assessment

Three additional endpoints will be analyzed in the FAS and PPS to investigate sensitivity to the disease assessment methodology:

- OR based on blinded central radiology assessment
- DC based on blinded central radiology assessment
- DOR based on blinded central radiology assessment

17.2.1. SECONDARY EFFICACY VARIABLES & DERIVATIONS

17.2.1.1. Progression-Free Survival Based on Blinded Central Radiology Assessment

Progression-free survival based on the blinded central radiology assessment is defined as the time from the date of randomization to the earliest of documented disease progression as defined by RECIST v 1.1, as recorded by the central radiologist, or death from any cause. Subjects for whom death or progression are not observed will be censored.

PFS will be calculated in months as (the earliest date of progression, death, or censoring, minus the randomization date, plus 1) divided by 365.25 days per year, times 12 months per year. PFS in tables and listings will be displayed to the closest 1/10 of a month.

17.2.1.2. Overall Survival

Overall survival is defined as the time from the date of randomization until the date of death from any cause. Subject death information is collected on the Serious Adverse Event and Survival Follow-Up eCRFs.

Subjects for whom death is not observed will be censored using the Censoring Rules (Set 5) presented in Table I (Section 17.2.2.2). OS will be calculated in months as (the earliest date of death or censoring, minus the randomization date, plus 1) divided by 365.25 days per year, times 12 months per year. OS in tables and listings will be displayed to the closest 1/10 of a month.

17.2.1.3. Objective Response Based on Investigator's Radiographic Assessment

The primary determination of objective response (OR) is based on the investigator's radiographic assessment of tumor response. OR is defined as a best overall response of Complete Response (CR) or Partial Response (PR). A best response of CR or PR must be confirmed no less than 28 days after the criteria for response are first met.

17.2.1.4. Disease Control Based on Investigator's Radiographic Assessment

The primary determination of disease control (DC) will be based on the investigator's radiographic assessment of tumor response. DC is defined as a best overall response of Complete Response (CR), Partial Response (PR), or at least 6 months of Stable Disease (SD) after the date of randomization.

17.2.1.5. Duration of Objective Response Based on Investigator's Radiographic Assessment

The primary determination of duration of objective response (DOR) will be based on the investigator's radiographic assessment of tumor response. The DOR is defined as the time in months from the date of the first response of CR or PR, whichever is first recorded and subsequently confirmed, to the earlier of the date of first documented progressive disease or the date of death due to any cause. Subjects for whom death or progression are not observed will be censored.

DOR will be calculated using the date of first documented progressive disease, death, or censoring as the end date of the objective response. The Censoring Rules (Set 1) from Section 17.1.2.1 will be applied. The calculation of DOR will be the date of the end of objective response minus the date of first confirmed response plus 1 day, divided by 365.25 days per year, times 12 months per year. DOR in tables and listings will be displayed to the closest 1/10 of a month.

17.2.1.6. OR, DC, and DOR Based on Blinded Central Radiology Assessment

The OR, DC, and DOR will be derived using the blinded central radiography assessment of tumor response. Definitions and derivations are otherwise the same as described for the OR, DC, and DOR based on the investigator’s assessment of tumor response (Section 17.2.1.3, Section 17.2.1.4, and Section 17.2.1.5, respectively).

17.2.2. MISSING DATA METHODS FOR SECONDARY EFFICACY VARIABLES

17.2.2.1. Progression-Free Survival Based on Blinded Central Radiology Assessment

The Censoring Rules (Set 1) which were presented in Section 17.1.2.1 will apply to PFS based on the blinded central radiology assessment of tumor response.

17.2.2.2. Overall Survival

Subjects who have not died will be right-censored as shown in Table I.

Table I. Overall Survival Censoring Rules (Set 5): Date of Progression or Censoring

Situation	Date of Death or Censoring	Outcome
Any death	Actual date of death	Death
No death and no post-baseline contact	Actual date of randomization	Censored
No death and at least 1 post-baseline-up	Actual date of last subject contact [1]	Censored

[1] The latest of all post-baseline assessment dates where the subject was physically alive, e.g. disease assessment visit, blood draw, non-fatal AE start/end date, dosing visit, date last reported alive, etc.

17.2.2.3. Objective Response Based on Investigator’s Radiographic Assessment

If the best overall response is missing or not evaluable, the subject will be classified as not having an objective response and will only be counted in the denominator for calculating ORR.

17.2.2.4. Disease Control Based on Investigator’s Radiographic Assessment

If the best overall response is missing, the subject will be classified as not achieving disease control and will only be counted in the denominator for calculating DCR.

17.2.2.5. Duration of Objective Response Based on Investigator’s Radiographic Assessment

Subjects who experience a response and do not experience death or progression after that response will have a censored PFS time. The Censoring Rules (Set 1) will be applied prior to calculating the duration of response.

17.2.2.6. OR, DC, and DOR Based on Blinded Central Radiology Assessment

Imputation of missing values for the OR, DC, and DOR based on the blinded central radiology review will be the same as for the OR, DC, and DOR based on the investigator assessment. The censoring rules (Set 1) will be applied to DOR based on central radiology review.

17.2.3. ANALYSES OF SECONDARY EFFICACY VARIABLES

All secondary efficacy variables will be analyzed in the FAS and PPS.

17.2.3.1. Progression-Free Survival by Blinded Central Radiology Assessment

The analysis methods and models that were used for the primary analysis will be applied to the PFS assessment by the blinded central radiology reviewer, using Censoring rules Set 1.

17.2.3.2. Overall Survival

Overall survival will be analyzed using the same statistical methodology as described for PFS based on the Blinded Central Radiology assessment in Section 17.2.3.1, except that Censoring Rules Set 5 will apply and the statistical tests will be 2-sided, conducted at a 0.05 level of significance.

17.2.3.3. Objective Response Rate Based on Investigator's Radiographic Assessment

A Cochran-Mantel-Haenszel analysis of the ORR, stratified for baseline ECOG-PS and number of prior systemic therapies for RCC, will be conducted at a two-sided significance level of 0.05. The stratified Mantel-Haenszel estimate of the odds ratio for experiencing objective response, with the axitinib arm as the reference level, will be reported as a measure of relative treatment effect, along with its two-sided 95% CI. Homogeneity among the 4 strata will be examined using a two-sided Breslow-Day test, conducted at a significance level of 0.05.

The ORR will also be summarized with estimates for each treatment group, overall and by stratum, based on the crude proportion of subjects who have a best overall response of CR or PR. The Clopper-Pearson method will be used to calculate exact two-sided 95% CIs for each crude rate.

17.2.3.4. Disease Control Rate Based on Investigator's Radiographic Assessment

The disease control rate (DCR) will be analyzed using the same methods as for ORR (Section 17.2.3.3).

17.2.3.5. Duration of Objective Response Based on Investigator's Radiographic Assessment

The duration of response as assessed by the investigator will be analyzed using the same statistical methodology as described for PFS based on the Blinded Central Radiology assessment in Section 17.2.3.1. Subjects who do not experience an objective response and therefore have no duration of objective response will be excluded from the analyses.

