Duration of objective response (DOR) is defined as the time from the date of the first response of CR or PR (whichever is first recorded), and subsequently confirmed, to the first date of documented progressive disease or death due to any cause. The DOR will be summarized descriptively using the 25th, 50th and 75th percentile (and 95% CI) of the Kaplan-Meier curve for subjects who have best overall response of confirmed CR or PR, by treatment group, both overall and within randomization strata. The DOR will be censored using the same censoring rules, whenever applicable, as PFS.

Each of the secondary endpoints described above will be performed for the FAS and PPS. For the purpose of hypothesis generation, subgroup may be performed for selected baseline characteristics.

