6.7. STATISTICAL TESTS

The primary analysis of the primary endpoint will be conducted using a one-sided test with a 0.1 significance level. All other PFS analyses will be conducted using one-sided tests with a 0.1 significance level also. Secondary endpoints such as OS, ORR, DCR, and DOR will be analyzed using two-sided tests with a significance level of 0.05.

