17.1.3. PRIMARY ANALYSIS OF PRIMARY EFFICACY VARIABLE

The primary objective of this study is to test the hypothesis that PFS is superior (longer) for subjects treated with AGS-16C3F than for subjects treated with axitinib.

The primary analysis of PFS based on the investigator's assessment of disease will be performed in accordance with the ITT principle in the FAS. All subjects who undergo randomization will be included in the primary analysis and grouped according to the treatment groups assigned by randomization. The Censoring Rules (Set 1) which are presented in Section 17.1.2.1 will be used to derive the event status and PFS times.

The difference between treatment groups will be tested using a stratified log rank test at a one-sided 0.1 significance level. The stratification factors will be the ECOG PS and the number of prior systemic RCC regimens, without any other covariate(s). If the direction of the difference between treatment arms favors AGS-16C3F, then the observed significance level (p-value) of the 1-sided test of superiority of AGS-16C3F will be calculated as $0.5 * p$ -value from a two-sided log-rank test (corresponding to a chi-squared test with d.f.=1). If the direction of the difference favors axitinib, then the observed significance level will be calculated as $(1 - (0.5 * p\text{-value from the two-sided log-rank test}))$.

Kaplan-Meier survival curves for the primary analysis variable will be produced, overall and by stratum. The following descriptive statistics will be reported in a table, overall and by stratum:

- Progression status:
 - Number and percent of subjects with observed disease progression per RECIST
 - Number and percent of subjects who died without disease progression beforehand
 - Number and percent of censored subjects
- Number and percent of censored subjects, by reason for censoring
- Estimated progression-free survival time (months), including the minimum, 25th percentile, 50th percentile (median), 75th percentile, and maximum. The 2-sided 95% CIs for the 25th, 50th, and 75th percentiles, calculated using Greenwood's formula for the standard error, will also be reported.

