The overall adjusted hazard ratio (HR) for AGS-16C3F relative to axitinib will be estimated using a proportional hazards (PH) model that includes terms for treatment effect and a stratification factor based on the baseline ECOG PS and the number of prior systemic RCC regimens (see section 7.1.1), and no other covariate. Ties will be addressed using Efron's (1977) method.

The model-based estimates for the HR and its corresponding one-sided 90% CI (upper confidence bound) will be reported. A two-sided 95% CI will also be reported in the clinical study report.

Hazard ratio estimates by stratum will be obtained from a PH model containing treatment, the stratification factor, and a treatment-by-stratum- interaction term. Homogeneity in the hazard ratios among strata will be examined by Wald's test. Results from a PH model without stratification will be reported also.

The adequacy of the model(s) will be evaluated, including an assessment of the proportional hazards assumption, as described in Section 17.1.6, "Exploratory Analyses".

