17.2.3.6. OR, DC, and DOR Based on Blinded Central Radiology Assessment

The OR, DC, and DOR based on blinded central radiology reviewer's assessment will be analyzed using the same statistical methods as the OR, DC, and DOR based on the investigator's assessment, respectively.

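### SAP 17.2.3.5 tests duration of response between arms in responders only, a comparison that randomization does not protect; the protocol's own text for this endpoint is descriptive

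*SAP*

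**What the plan says.** No between-arm test of DOR is named in SAP 17.2.3.5 itself. It is reached by cross-reference:

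- SAP 17.2.3.5: "The duration of response as assessed by the investigator will be analyzed using the same statistical methodology as described for PFS" by central review in 17.2.3.1. On the population: "Subjects who do not experience an objective response and therefore have no duration of objective response will be excluded from the analyses".
- SAP 17.2.3.6 extends this to central-review DOR, which under that reader's "assessment will be analyzed using the same statistical methods as the OR, DC, and DOR based on the" investigator's reading.
- SAP 17.2.3.1: "The analysis methods and models that were used for the primary analysis will be applied to the PFS assessment" of the central reviewer.
- SAP 17.1.3, where the chain ends: "The difference between treatment groups will be tested using a stratified log rank test at a one-sided 0.1 significance level". It adds a stratified Cox hazard ratio, and then "Hazard ratio estimates by stratum will be obtained from a PH model containing treatment", stratum and their interaction, with a Wald homogeneity test and an unstratified model.
- SAP 6.7 confirms that a test is meant: "Secondary endpoints such as OS, ORR, DCR, and DOR will be analyzed using two-sided tests with a significance level of 0.05".
- SAP 17.2.3 applies all secondary analyses to both the FAS and the PPS.

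Protocol 7.4.2 (version 6.0) treats DOR differently: "The DOR will be summarized descriptively using the" 25th, 50th and 75th Kaplan-Meier percentiles with 95% CI, among confirmed responders, by arm, overall and within randomization strata. The synopsis likewise speaks only of a summary. In the same section, central-review PFS and OS take the primary methodology, and ORR and DCR get a Cochran-Mantel-Haenszel test. More general wording points the other way: protocol 7.4 mentions inferential comparison of secondary endpoints when it fixes the strata, and 2.3.2 lists DOR among endpoints compared with axitinib.

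**The concern.** Response happens after randomization and treatment can affect it. Once non-responders are dropped, each arm is represented by the patients whom that drug made respond, and these can be different kinds of patient. A p-value or hazard ratio for DOR can then favour one arm because of who responded, with no difference in how long a given patient's response lasts. The stratification factors were balanced at randomization across all subjects. Conditioning on them among responders adjusts for those two factors only.

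The documents make a different responder mix plausible. Protocol 2.2.1 says non-clear cell tumours differ from clear cell tumours in sensitivity to anti-VEGF treatment. Axitinib acts on VEGF receptors and AGS-16C3F on ENPP3. Non-clear cell subjects are selected for ENPP3 positivity and clear cell subjects are not. Up to 26 of 134 subjects (26/134 = 19%) may be non-clear cell, yet histology is left out of the analysis strata.

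At stake is how DOR is reported and read. The primary PFS comparison uses all randomized subjects and is untouched.

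**Working it through.** **1. The plan's own figure.** SAP 3.5 sizes the trial for PFS only. Events = 4(1.2816 + 0.8416)² / (ln 0.667)² = 110 for 80% power at one-sided 0.1, which matches the plan. There is no sizing for DOR.

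**2. Responders.** The only response rate in the documents is 3/13 = 23% (Phase 1, AGS-16C3F at the Phase 2 dose; protocol 1.4). No axitinib rate is given. Assuming 10–23% in both arms: 134 × 0.10 = 13.4 and 134 × 0.23 = 30.8, so about 13 to 31 responders in total.

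**3. Power.** Suppose every responder had a DOR event and the DOR hazard ratio were 0.667. Power at two-sided 0.05 would then be at most about 11% (13 events) to 20% (31 events). For 80% power, 4(1.96 + 0.8416)² / (ln 0.667)² = 191 events are needed, more than the 134 subjects.

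**4. Rejection with no effect on duration.** A simulation with assumed inputs:
- 67 subjects per arm, in two equal prognosis classes;
- exponential DOR with medians of 12 and 4 months, the same in both arms;
- censoring uniform over 4–20 months;
- four strata from two binary factors, each matching the prognosis class with probability m (m = 0.5 means unrelated);
- stratified log-rank test in responders, rejecting when |Z| > 1.96.

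Overall response is 23% in both arms in every row; only the mix by class changes (20,000 trials per cell, Monte Carlo SE at most 0.3 points).

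| Responder mix | Response in good/poor class, axitinib vs AGS-16C3F | Good-class share of responders | m = 0.5 | 0.70 | 0.75 | 0.80 |
|---|---|---|---|---|---|---|
| Same | 36/10 vs 36/10% | 78% vs 78% | 5.4% | 5.3% | 5.0% | 5.4% |
| Mild | 36/10 vs 30/16% | 78% vs 65% | 5.9% | 5.8% | 5.8% | 5.5% |
| Moderate | 36/10 vs 23/23% | 78% vs 50% | 9.1% | 7.4% | 6.8% | 5.9% |
| Extreme | 44/2 vs 23/23% | 96% vs 50% | 16.0% | 11.4% | 9.9% | 8.3% |

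Swapping the arms in the extreme row gives 15.5/11.3/9.4/8.3%. Mean DOR events are 17.2–18.7. In the moderate and extreme rows most rejections favour the arm whose responders have the better prognosis.

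At a 10% response rate (5,000 trials, SE at most 0.4 points, mean events 7.4–8.1), m = 0.5 and 0.75 give: same mix 5.4% and 4.9%; moderate (16/4 vs 10/10%) 6.5% and 5.7%; extreme (19/1 vs 10/10%) 7.8% and 6.3%.

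A simpler simulation, unstratified and without censoring, in which one drug's responders were mostly good-prognosis, gave 7–10%.

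**5. Precision.** SE(log HR) ≈ 2/√d, so an estimate of 1.0 has 95% limits exp(±1.96 × 2/√d).
- d = 7: exp(1.96 × 0.756) = 4.40, interval 0.23–4.40.
- d = 17: exp(1.96 × 0.485) = 2.59, interval 0.39–2.59.
- By stratum, if the four strata are equal: d = 1.75 gives 0.05–19.4; d = 4.25 gives 0.15–6.7.

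**6. Level.** SAP 17.2.3.5 leads through 17.2.3.1 to the one-sided 0.1 of 17.1.3. SAP 17.2.3.2 overrides that for OS with two-sided 0.05; 17.2.3.5 has no such override. SAP 6.7 assigns DOR two-sided 0.05. The rates in step 4 apply to two-sided 0.05 only.

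**The case against.** The strongest reply is that little turns on this. SAP 7.4 makes secondary p-values nominal, admits limited power and promises to acknowledge type 1 error inflation. Every simulation input except 3/13 is assumed. Protocol 7.4 groups prior-regimen categories on the assumption of similar prognosis, and if the strata do track prognosis, rejection stays at 5.9–7.4% even for a moderate difference in mix. The 16% figure needs an extreme mix and strata unrelated to prognosis. All of that stands and limits the size of the point. But the SAP 7.4 caveat concerns multiplicity and power; it does not tell a reader that the arms compared are selected subsets.

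Second, the protocol does not forbid a comparison, given the general wording in 7.4 and 2.3.2. That also stands. The 7.4 sentence fixes strata and names no DOR test, so the specific DOR text is the better guide.

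Third, a descriptive summary by arm carries the same selection, so deleting the test does not remove the bias. That is correct, and it is why a table note is needed as well. A lighter remedy would be to keep the test, state one level and label it exploratory and non-randomized. That would inform readers, but it keeps hazard ratios that carry almost no information.

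A reader might infer that the SAP departed from its protocol without logging it, because the only SAP Table A entry for protocol 7.4.2 is the switch from relative risk to odds ratio. The documents do not support that. The SAP (final version June 2019) is based on protocol version 4.0, which is not supplied. Version 6.0 is dated August 2020, so the SAP could not have logged a difference from it.

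**Conclusion.** The point holds as a matter of method: the SAP plans a between-arm test and hazard ratios for DOR in a subset defined by a post-randomization outcome, with no caveat. Against the supplied protocol the specific DOR text is descriptive; whether the SAP matched version 4.0 cannot be checked, so the missing Table A entry is not an established defect. The test level is inconsistent within the SAP.

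At a 23% response rate and two-sided 0.05, false rejection is about 5–6% for the same or a mildly different responder mix, 6–9% for a moderate difference and 8–16% for an extreme one; at 10% it does not exceed 7.8%. The extreme case is an upper end, not an expectation. These figures rest on assumed response rates, prognosis classes, DOR medians and censoring. A reader might infer a seriously inflated error rate or a threat to the trial's conclusion. Neither follows: inflation is small unless the mixes differ clearly, and the primary PFS test and its error rate are unaffected. The change should be made, but it concerns the reporting of one secondary endpoint.

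**What to change.** - **SAP 17.2.3.5**, and 17.2.3.6 if central-review DOR is still analysed (protocol 5.5 now has scans read on site): report only Kaplan-Meier 25th, 50th and 75th percentiles with 95% CI among confirmed responders, by treatment group, overall and within randomization strata as in protocol 7.4.2, for FAS and PPS. Remove the between-arm test, the hazard ratio and the by-stratum hazard ratios.
- **SAP 6.7**: delete DOR from the tested endpoints. This also removes the conflict over the level.
- **DOR tables**: add a note that the by-arm summaries describe responder subsets and are not a randomized comparison.

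The cost is SAP wording, one note, and the loss of up to four sets of nominal DOR p-values and hazard ratios (investigator and central review, each in FAS and PPS), with their homogeneity tests and unstratified models. The 110 events, the 134 subjects and the alpha do not change, and the ORR and PFS comparisons between the randomized arms remain.

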17.2.3.6. OR, DC, and DOR Based on Blinded Central Radiology Assessment

The OR, DC, and DOR based on blinded central radiology reviewer's assessment will be analyzed using the same statistical methods as the OR, DC, and DOR based on the investigator's assessment, respectively.

17.2.3.7. Concordance of Disease Assessments by Independent Reviewers

The best overall response, objective response, and disease control determinations made by the investigator will be compared to the consensus determinations of the blinded central reviewers. Additionally, determinations made by the two radiologists who conducted the blinded central review will be compared.

These concordance analyses will be performed by treatment group and overall. For each analysis, the number and percentage of subjects for whom the assessors were in agreement will be presented.

